5 STUDY ACTIVITIES

5.1 Eligibility Criteria

Subjects must meet all of the following criteria to be included in the study. Anything other than a positive response to the questions below will result in exclusion from study participation.

Consent

- 1. Subject must voluntarily **sign and date an informed consent**, approved by an independent ethics committee (IEC)/institutional review board (IRB), prior to the initiation of any screening or study-specific procedures.

Demographic and Laboratory Assessments

- 2. Adult **male or female**, at least 18 years old at time of the baseline visit.
- 3. **Laboratory values** meeting the following criteria within the screening period prior to the first dose of study drug:
 - Hemoglobin \geq 8 g/dL;
 - Serum aspartate transaminase (AST) and alanine transaminase (ALT) $\leq 2 \times$ upper limit of normal (ULN).
- 4. Are willing and able to comply with procedures required in this protocol.

- ✓ 5. Estimated glomerular filtration rate (eGFR) calculated by Cockcroft-Gault ≥ 90 mL/min at the Screening visit.

Disease/Condition Activity

- ✓ 6. Diagnosis of UC for at least 90 days prior to Baseline. Appropriate documentation of biopsy results consistent with the diagnosis of UC in the assessment of the investigator, must be available prior to enrollment.
- ✓ 7. Subject meets the following disease activity criteria: Active UC with an Adapted Mayo score of 5 to 9 points and ESS of 2 to 3 (confirmed by central review prior to enrollment).

Subject History

- ✓ 8. Subject must not have an active, chronic, or recurrent infection that based on the investigator's clinical assessment makes the subject an unsuitable candidate for the study, or the following:
 - Subject must not currently be positive with *C. difficile* toxin as identified during Screening or another known intestinal pathogen;
 - Subject must not be infected with human immunodeficiency virus (HIV);
 - Subject must not have active hepatitis B or hepatitis C (as defined in the Operations Manual);
 - Subject must not have evidence of active tuberculosis (TB) or meet TB exclusionary parameters (See specific requirements for TB testing in Section 3.13 of the Operations Manual).

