- ✓ 30. Subject must not receive treatment with rectal aminosalicylates or corticosteroids, other enemas/suppositories (other than required for endoscopy prep), within 14 days prior to the Screening endoscopy and during the remainder of the Screening Period.
- ✓ 31. Subject must not receive any parenteral nutrition within 30 days prior to Baseline.
- ✓ 32. Subject must not receive fecal microbial transplantation within 30 days prior to Baseline.
- ✓ 33. Subject must not receive IV anti-infectives within 30 days prior to Baseline visit or oral/intramuscular (IM) anti-infectives (non-UC-related) within 14 days prior to the Baseline visit.
- ✓ 34. Subject must not have been treated with any investigational drug within 30 days or 5 half-lives of the drug (whichever is longer) prior to the first dose of study drug or is currently enrolled in another clinical study.
- ✓ 35. Subject must not have received systemic treatment with known cytochrome P450 (CYP)3A inhibitors or CYP3A inducers within 30 days of the Screening Period and through the end of the study.
- ✓ 36. Subject must not have received any live vaccine, with the exception of non-replicating live viral vaccines such as the Jynneos vaccine, within 30 days prior to the first dose of study drug, or expected need of live vaccination during study participation including at least 30 days after the last dose of study drug.

Contraception and Pregnancy

- ✓ 37. For all females of child-bearing potential; a negative serum pregnancy test at the Screening Visit and a negative urine pregnancy test at Baseline prior to the first dose of study drug.
- ✓ 38. Female subjects of childbearing potential must practice at least 1 protocol-specified method of birth control, that is effective from Study Day 1 through at least 30 days after the last dose of study drug. Female subjects of non-childbearing potential do not need to use birth control.
- ✓ 39. Female who is not pregnant or breastfeeding and is not considering becoming pregnant or donating eggs during the study or for approximately 30 days after the last dose of study drug.

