Subjects with a known history of HIV infection are excluded from study participation. HIV testing will be conducted as part of the infection screening at the Screening visit. The investigator must discuss any local reporting requirements to local health agencies with the subject. The site will report these results to their health agency per local regulations, if necessary. If a subject has a confirmed positive result, the investigator must discuss with the subject the potential implications to the subject's health and subjects should be referred for clinical care promptly. A subject will not be eligible for study participation if test

results indicate a positive HIV infection. This testing is to be done at the central lab. AbbVie will not receive results from the testing and will not be made aware of any positive result.

Stool Sample Testing

If the investigator has a reasonable suspicion of a gastrointestinal infection, they should ensure this has been excluded prior to screening the subject.

Fecal Calprotectin

Fecal calprotectin (FCP) will be performed at the study visits indicated in Section 2.1. Subjects will be sent home with a stool sample supply kit and the site will give instructions to assist with collection procedures. If the FCP sample is collected during the Screening period, it may be used as the Baseline. All stool samples should be collected before any bowel preparation for endoscopy is started and returned to the site within 3 days of collection.

C. Difficile Stool Testing

During the Screening period a stool sample will be collected and sent to the central laboratory for testing. The sample will be assessed for the presence of *C. difficile* toxin. Subjects who are positive for *C. difficile* toxin may be treated appropriately and re-screened.

The sample must be shipped to the central laboratory using dry ice.

High-Sensitivity C-Reactive Protein (hs-CRP)

Blood samples for hs-CRP will be obtained at the study visits indicated in Section 2.1.

State of Emergency or Pandemic-Related Acceptable Protocol Modifications

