3.16 Additional Assessments as Required

Endoscopy

Endoscopy at/during Screening will be required to calculate the Mayo endoscopy subscore (confirmed by a central reader) at Baseline. Endoscopic evaluations using Mayo endoscopic score confirmed by central reader will be done at Screening, Week 8 and Week 16.

The same endoscopist, where possible, should perform all endoscopies. In addition, where possible, the investigator or sub-investigator should be the endoscopist for the study. It is expected that all subjects who remain in the study through at least Week 6 will have a Week 8 endoscopy.

A full colonoscopy will be performed at Screening unless the subject underwent a full colonoscopy within 12 months prior to Screening. There must be appropriate documentation available to confirm the diagnosis, extent of disease, and to exclude dysplasia and colon cancer. If this is available, the screening endoscopy may be either a full colonoscopy or a flexible sigmoidoscopy. All other endoscopies may be flexible sigmoidoscopies or colonoscopies at the discretion of the investigator.

All endoscopies will be performed and recorded at the site in a video format. Videos from subjects with eligible Mayo endoscopic subscores during Screening and all videos from subjects at Week 8 and Week 16 will be sent to a central review vendor and scored as described in the central review charter. Endoscopies will be evaluated using the Mayo endoscopic subscore. The Mayo endoscopic subscore, including the presence or absence of friability will be documented by the endoscopist at the site and maintained in the subject's source documents. If, in the assessment of the site endoscopist, the Screening endoscopy does not indicate an endoscopy subscore of 2 or 3 or the extent of inflammation is

limited to the rectum, per eligibility requirements, the subject should be screen-failed and the video should not be sent for central reading.

There will be a window of \pm 7 days to conduct the endoscopy. This window may be extended as necessary after consultation with the AbbVie TA MD in case of external, not subject-related circumstances (e.g., scheduling conflict).

Intestinal Biopsy

Mandatory biopsies will be collected during endoscopies occurring during Screening, Week 8, and Week 16 as described below:

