3.17 Rescreening

Subjects who initially screen fail for the study may be permitted to re-screen following re-consent. The subject must meet all the eligibility criteria as assessable at the time of re-screening to qualify for the study. There is no minimum period of time a subject must wait to re-screen for the study.

If the subject had a complete initial screening evaluation including the TB test, Hepatitis B virus (HBV), Hepatitis C virus (HCV), human immunodeficiency virus (HIV), electrocardiogram (ECG), and chest x-ray these tests will not be required to be repeated for re-screening provided the conditions noted in Section 3 are met and no more than 90 days have passed.

If a subject is being rescreened \leq 14 days from the date of the previous screening testing, it is not required to repeat testing for chemistry/hematology, urinalysis, serum pregnancy, and C. difficile provided that the subject's health status has not changed to warrant a repeat test. If a subject is being rescreened more than 14 days (> 14 days have passed) from the collection date of the previous screening laboratory testing then chemistry/hematology, urinalysis, serum pregnancy, and C. difficile should be repeated during rescreening.

[figure not shown]
An endoscopy with biopsy will not be required to be repeated for re-screening provided the conditions noted in Section 3.16 are met and the endoscopy is within 45 days of the Baseline visit. All other screening procedures will be repeated unless otherwise stated above. Sites may contact the AbbVie TA MD if there are questions on if subjects should or should not be re-screened.

All subjects need to have their average daily Stool Frequency subscore, average daily RBS, and Adapted Mayo score calculated to verify eligibility criteria before randomization at Baseline.

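### The re-screening rules let an endoscopy done while a subject was *C. difficile* toxin-positive stand as the Baseline ESS after the infection has been treated

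*Protocol*

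**What the plan says.** - **Entry.** Criterion 8 (Protocol 5.1) excludes a subject currently positive for "toxin as identified during Screening or another known intestinal pathogen". Criterion 7 requires a centrally confirmed ESS of 2 to 3 and an Adapted Mayo score of 5 to 9.
- **After a positive test.** Operations Manual 3.13: "Subjects who are positive for *C. difficile* toxin may be treated appropriately and re-screened".
- **Re-use of the endoscopy.** Operations Manual 3.17: "An endoscopy with biopsy will not be required to be repeated for re-screening provided the conditions noted in Section 3.16 are met". A second condition limits its age to 45 days before Baseline. On waiting time, the same section states: "There is no minimum period of time a subject must wait to re-screen for the study".
- **Source of the Baseline ESS.** Operations Manual 3.16: "Endoscopy at/during Screening will be required to calculate the Mayo endoscopy subscore (confirmed by a central reader) at Baseline". SAP 7.1 takes as Baseline the last non-missing value before the first dose.
- **Washout.** Criterion 33 bars oral or intramuscular "anti-infectives (non-UC-related) within 14 days prior to the Baseline visit", and intravenous ones within 30 days.
- **Endpoint and control.** The primary endpoint is an absolute ESS of 0 or 1 at Week 8 (Protocol 3.2). The comparison is with historical placebo only (Protocol 4.2).

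**The concern.** The toxin sample and the endoscopy are both Screening procedures. Stool must be collected before bowel preparation, but nothing requires the toxin result to be known before the endoscopy. A subject can therefore have the endoscopy, learn of a positive toxin test, be treated, re-screen and keep that endoscopy.

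Because the endpoint is absolute, only the ESS 2-3 check at entry makes a Week 8 responder someone who has improved. If infection contributed to the ESS at that check, the colon may already be better at the first dose. A Week 8 ESS of 0 or 1 would still be credited to ABBV-668, and no concurrent arm shares the effect. The secondary endpoints that use ESS are exposed too. Clinical response per Adapted Mayo score uses the carried-over Baseline ESS directly in its change from Baseline.

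**Working it through.** **1. Does any condition block the re-use?** In Operations Manual 3.17, the proviso about unchanged health status attaches to chemistry/hematology, urinalysis, serum pregnancy and *C. difficile* testing. It does not attach to the endoscopy. Section 3.16 covers colonoscopy history, video, central reading, the timing window and biopsies. It does not ask that the endoscopy be free of infection or follow its treatment. An infected colon scoring 2 or 3 beyond the rectum meets it.

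**2. Does the timing allow it?** Days left between the endoscopy and the start of washout, for the toxin result and treatment:
- oral or intramuscular anti-infectives: 45 − 14 = 31 days;
- intravenous anti-infectives: 45 − 30 = 15 days.

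**3. What is carried over and what is re-measured?** Section 3.17 requires the stool frequency subscore (SFS), the rectal bleeding subscore (RBS) and the Adapted Mayo score to be calculated at Baseline. Operations Manual 8.2 takes SFS and RBS from the 7 days before the visit. Those days lie inside the 14-day washout, so they follow treatment. Only ESS and histology are old. To reach an Adapted Mayo score of 5, the subject still needs:
- with ESS 3: SFS + RBS ≥ 5 − 3 = 2;
- with ESS 2: SFS + RBS ≥ 5 − 2 = 3.

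Current symptoms are therefore required. Current endoscopic disease is not checked again.

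**4. How much could one subject matter? (Illustration only.)**

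Inputs from the documents: n = 40; ABBV-668 prior Beta(0.5, 0.5); sample-size criterion P(difference > 0 | data) > 0.90 (Protocol 7.8, SAP 2.4).

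Assumed, because the documents redact or do not give them:
- placebo rate p of 5%, 8%, 10% or 12%;
- placebo prior Beta(wp, w(1 − p)) with weight w = 59, 330 or 562. SAP Table D-1 suggests the range: Beta(20.9, 38.4) has weight 20.9 + 38.4 = 59.3 from 154 + 174 = 328 subjects, and 122 + 112 + 154 + 174 = 562 is the sum of the four denominators;
- chance q of ESS 0/1 in the affected subject of 50% to 80%.

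*The plan's own figure.* With a true increase of 30 points, the probability of meeting the criterion is 98.1% to 99.99% over placebo rates of 5% to 20% and prior weights of 30 to 560. That agrees with the stated figure of more than 90%.

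*No drug effect.* Let r be the smallest number of responders out of 40 that meets the criterion. False success is P(Bin(40, p) ≥ r). With one affected subject it is q·P(Bin(39, p) ≥ r − 1) + (1 − q)·P(Bin(39, p) ≥ r).

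Example, p = 10% and w = 330 or 562, so r = 7: no affected subject gives 0.100. One at q = 0.5 gives 0.5 × 0.1903 + 0.5 × 0.0894 = 0.140. One at q = 0.8 gives 0.8 × 0.1903 + 0.2 × 0.0894 = 0.170.

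| p | w = 59: r | none | one (q 0.5 to 0.8) | w = 330 or 562: r | none | one (q 0.5 to 0.8) |
|---|---|---|---|---|---|---|
| 5% | 5 | 0.048 | 0.086 to 0.112 | 4 | 0.138 | 0.219 to 0.273 |
| 8% | 7 | 0.038 | 0.061 to 0.077 | 6 | 0.097 | 0.143 to 0.177 |
| 10% | 8 | 0.042 | 0.063 to 0.079 | 7 | 0.100 | 0.140 to 0.170 |
| 12% | 9 | 0.044 | 0.063 to 0.079 | 8 | 0.100 | 0.135 to 0.162 |

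The expected response rate moves by (q − p)/40, from (0.50 − 0.12)/40 = 0.95 points to (0.80 − 0.05)/40 = 1.9 points per affected subject.

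**The case against.** Several safeguards narrow the path. Suspected gastrointestinal infection is to be excluded before screening. Biopsies to rule out infection are allowed at any endoscopy. The toxin test is repeated if re-screening is more than 14 days later. Sites may consult the sponsor's medical director about re-screening, and may repeat the endoscopy if they choose. The post-treatment symptom requirement in step 3 will remove some subjects whose activity was mainly infection. All of this stands and makes the case uncommon. None of it requires a new endoscopy, and exclusion on suspicion misses the unsuspected positive.

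The magnitude is assumption-driven. The documents give no source for the 50-80% and no *C. difficile* frequency. The 0.90 cut-off is a sample-size criterion; Protocol 7.4 and SAP 9.3.2 report a posterior probability and credible interval and set no success threshold. That also stands, so the figures only show scale.

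Three stronger readings are tempting, but the documents do not support them:
- *The whole Adapted Mayo score comes from the infected colon.* It does not: SFS and RBS are re-measured after treatment.
- *Fecal calprotectin is carried over as well.* Section 3.13 lets a Screening sample serve as Baseline. But 3.17 repeats every screening procedure it does not waive, calprotectin is not waived, and the activities schedule places it at Baseline.
- *The trial is known to be biased towards ABBV-668.* No such subject need exist, and the historical trials may have had a similar practice.

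**Conclusion.** The gap is real but narrow. Operations Manual 3.13 and 3.17, read together, allow an endoscopy from a toxin-positive period to supply the Baseline ESS, the ESS entry check and the Baseline histology after the infection has been treated. If such a subject were enrolled and the ESS fell because the infection cleared, the trial would count a response that ABBV-668 did not cause.

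Under the assumptions in step 4, one affected subject raises false success by a factor of roughly 1.3 to 2.3 (0.135/0.100 to 0.112/0.048). The absolute level depends heavily on the redacted prior: 0.061-0.112 at weight 59, against 0.135-0.273 at weights 330 to 562. This is a cheap improvement worth making. It is not evidence that the result is wrong.

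**What to change.** 1. Reconcile Operations Manual 3.13 and 3.17: state that the 45-day carry-over does not apply to an endoscopy, with its biopsies, obtained while the subject was toxin-positive.
2. In 3.16, schedule the Screening endoscopy after the central toxin result is known. A positive result then normally comes before any endoscopy, so no extra procedure is needed.
3. If subjects are already enrolled, compare the dates of any positive toxin result, the Baseline endoscopy and the first dose. If any subject followed this path, report the number and add to SAP 9.3.3 a sensitivity analysis of the primary endpoint counting each as a non-responder.

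**Cost.** Items 1 and 2 take a sentence each, plus a short wait within Screening. The documents do not give the turnaround for the toxin result, but the Screening note in Operations Manual 2.1 already allows the 30-day period to be extended when test results are delayed. The SAP version history (version 2.0, September 2024) refers to enrolment in the past tense. If enrolment is over, item 3 is the useful part; it needs no new data collection. Counting the subject as a non-responder is one conservative choice among several, so it belongs in a sensitivity analysis and not in the main analysis.

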3.14 Subject Withdrawal

All attempts must be made to determine the date of the last study drug dose and the primary reason for discontinuation of study drug or study participation. The information will be recorded on the appropriate eCRF page. However, these procedures should not interfere with the initiation of any new treatments or therapeutic modalities that the investigator feels are necessary to treat the subject's condition. Following discontinuation of study drug, the subject will be treated in accordance with the

investigator's best clinical judgment, irrespective of whether the subject decides to continue participation in the study.

In the event a subject withdraws consent from the clinical study, biomarker research will continue unless the subject explicitly requests analysis to be stopped. When AbbVie is informed the subject has withdrawn and no longer wishes biomarker research to continue, samples will not be analyzed, no new biomarker analysis data will be collected for the withdrawn subject or added to the existing data or database(s), and the samples will be destroyed. A subject may withdraw consent for optional biomarker research at any time and remain in the clinical study. Data generated from clinical study and/or optional biomarker research, before subject withdrawal of consent, will remain part of the study results.

3.15 Unscheduled Visits

An Unscheduled Visit should be performed when the subject comes in for a medical visit for evaluation and assessment. During Unscheduled Visits, blood and urine samples may be obtained for the laboratory tests listed in Section 3.13 or for other tests at the investigator's discretion; physical examination (including neurological examination) may be performed at the investigator's discretion.

Visits for dispensing new study drug in case of temperature excursion, loss or damage are not considered an Unscheduled Visit. In addition, visits to only retest a lab will not be considered an Unscheduled Visit.

3.16 Additional Assessments as Required

Endoscopy

Endoscopy at/during Screening will be required to calculate the Mayo endoscopy subscore (confirmed by a central reader) at Baseline. Endoscopic evaluations using Mayo endoscopic score confirmed by central reader will be done at Screening, Week 8 and Week 16.

The same endoscopist, where possible, should perform all endoscopies. In addition, where possible, the investigator or sub-investigator should be the endoscopist for the study. It is expected that all subjects who remain in the study through at least Week 6 will have a Week 8 endoscopy.

A full colonoscopy will be performed at Screening unless the subject underwent a full colonoscopy within 12 months prior to Screening. There must be appropriate documentation available to confirm the diagnosis, extent of disease, and to exclude dysplasia and colon cancer. If this is available, the screening endoscopy may be either a full colonoscopy or a flexible sigmoidoscopy. All other endoscopies may be flexible sigmoidoscopies or colonoscopies at the discretion of the investigator.

All endoscopies will be performed and recorded at the site in a video format. Videos from subjects with eligible Mayo endoscopic subscores during Screening and all videos from subjects at Week 8 and Week 16 will be sent to a central review vendor and scored as described in the central review charter. Endoscopies will be evaluated using the Mayo endoscopic subscore. The Mayo endoscopic subscore, including the presence or absence of friability will be documented by the endoscopist at the site and maintained in the subject's source documents. If, in the assessment of the site endoscopist, the Screening endoscopy does not indicate an endoscopy subscore of 2 or 3 or the extent of inflammation is

limited to the rectum, per eligibility requirements, the subject should be screen-failed and the video should not be sent for central reading.

There will be a window of \pm 7 days to conduct the endoscopy. This window may be extended as necessary after consultation with the AbbVie TA MD in case of external, not subject-related circumstances (e.g., scheduling conflict).

Intestinal Biopsy

Mandatory biopsies will be collected during endoscopies occurring during Screening, Week 8, and Week 16 as described below:

- 8 biopsies will be collected at each time point from the region of most severe involvement as determined by endoscopic assessment. Biopsies will be used for histologic, gene expression and IHC/MOA analyses. For all biopsies, the segment from which the biopsy was collected should be documented during endoscopy. For biopsies collected for histologic analysis, the distance from anal verge should also be documented.
- 4 biopsies will be collected for histologic analysis:
 - 2 biopsies representative of the average degree of inflammation
 - 2 biopsies representative of the most inflamed intestinal tissue (if the area is ulcerated, the sample should be obtained from the edge of the ulcer)
- 2 biopsies will be collected for gene expression analysis:
 - 1 biopsy representative of the average degree of inflammation
 - 1 biopsy representative of the most inflamed intestinal tissue (if the area is ulcerated, the sample should be obtained from the edge of the ulcer)
- 2 biopsies will be collected for IHC/MOA analysis:
 - 1 biopsy representative of the average degree of inflammation
 - 1 biopsy representative of the most inflamed intestinal tissue (if the area is ulcerated, the sample should be obtained from the edge of the ulcer)
- The biopsies for histopathological, gene expression, and IHC/MOA analysis collected for the main study may also be used for biomarker research to assess and generate prognostic, predictive, pharmacodynamic, or surrogate biomarker signatures.

Additional biopsies as indicated:

- Appropriate documentation of biopsy results consistent with the diagnosis of UC, in the assessment of the investigator, must be available in order to confirm the subject's eligibility for the study. If this documentation is not available a diagnostic biopsy from the most affected observed area of the colon must be performed during the Screening endoscopy and read by a qualified local pathologist and the results reviewed by the investigator.
- Biopsies to rule out dysplasia, colon cancer and infection may be taken per the investigator's discretion during any endoscopy performed during this study and evaluated by the local

pathologist. The signed pathology report will be monitored by the responsible SMA and kept with the subject's source documents onsite.

Biopsy sampling should be recorded on the endoscopy video.

Unless endoscopic findings indicate otherwise, biopsies will be taken from the rectosigmoid segment of the colon at each visit with endoscopy.

If a diagnosis of high grade colonic dysplasia or colon cancer is discovered during any subsequent endoscopic evaluation during the course of the study, the findings should be recorded as an AE and the subject should be discontinued from the study. If low grade colonic dysplasia is discovered during any subsequent endoscopic evaluation during the course of the study, the findings should be entered as an AE and the subject may continue in the study if the lesion has been completely removed after discussion with the AbbVie TA MD.

Full Mayo Score, Adapted Mayo Score, Partial Adapted Mayo Score

Data from the subject diaries will be collected to calculate Full Mayo Score, Adapted Mayo Score (also referred to the modified Mayo Score), and Partial Adapted Mayo Score at the time points indicated in Section 2.1.

Whenever possible, the same physician (investigator or sub-investigator) should determine the Physician's Global Assessment (PGA) subscore for an individual subject through the duration of the study. The directions for capturing the stool frequency subscore, RBS, and PGA subscores of the Full Mayo Score, Adapted Mayo Score, and Partial Adapted Mayo Score are described in Section 8.2.

